This intervention trial will use a randomized factorial trial design where each of the 96 participants is randomly assigned to one of 16 combinations of the four study mini-interventions (IPs). There will be 16 possible combinations for the four IPs. For example, one combination will include no IP, and one combination will include all four IPs, and four combinations will include only one of the IPs. The rest of the 10 combinations will include a combination of two or three of the IPs (e.g. IP 1 + 2; IP 1 + 2 + 3; IP 2 + 3; IP 1 + 3, etc.) With n=6 individuals randomly assigned to each of the 16 combinations, this will yield n=48 with a given IP versus n=48 without the given IP (averaging over other combinations of the other three IPs) for the test of each main effect.

- 3. Describe the primary and secondary study endpoints:**

The primary endpoints are feasibility, usability, and acceptability of the IP.

The secondary study endpoint is change in help-seeking intention.

- 4. Provide a description of the following study timelines:**

Duration of an individual subject's active participation:

1 month

Duration anticipated to enroll all subjects:

1 year

Estimated date for the investigator to complete this study (complete primary analyses):

4/30/2024

- 5. List the inclusion criteria:**

Adolescents ages 14-19 will be included if they provide their assent and/or consent if 18 or above; have access to a smartphone; have finished 6th grade; have access to and intellectual and physical ability to use the internet; fit demographic criteria (SGMY); and have symptoms of depression and/or anxiety that are mild or more severe (PHQ-8 and/or GAD-7 = 5 or above)

We will routinely monitor the sample to ATTEMPT to reach close to the following proportions based on recruitment and enrollment flow (e.g. if recruitment and enrollment flow is at a steady rate and we have reached the proportions below we may begin to exclude those being oversampled to obtain balance - because of the pilot nature of the study this may not be possible if recruitment flow is slower than anticipated)

50% ages 14-16 and 50% ages 17-19

50% identify as sexual minority but cisgender and 50% identify as not cisgender

at least 40% identify as a racial or ethnic minority

- 6. List the exclusion criteria:**

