*** Identify the subgroups and provide a justification:**

Children under the age of 14 will not be included in study participation.

The intervention is specifically targeting adolescents in middle adolescence (high school age). This is a time period when they may seek mental health help without parental consent in some states (Pennsylvania) and the interventions will be designed for youth who may be able to seek help with or without parental support.

(Note: the interventions we are developing are not treatment interventions, they are interventions to promote help-seeking for actual mental health treatment in SGMY).

Subgroups will not be explicitly excluded in the beginning but once specific proportions are reached (see inclusion criteria), if the recruitment flow is adequate, we will then change our entry based on the proportion not yet reached. We may not be able to do this due to the pilot nature of this study. We aim to have at least 40% of our sample (38/96 individuals) represent a racial or ethnic minority, so once 60% of the sample (58/96 individuals) is recruited that identifies as not belonging to a minority, new interested participants will then begin to be excluded from then on.

8. Describe the power analysis used and cite your method of statistical analysis.

If a power analysis is not possible, thoroughly justify the sample size required for the study, including appropriate literature citation (alternatively provide page reference in attached protocol):

Participants (N=200) will be enrolled. (N=96 will be given baseline. With groups of n=6 randomly assigned to each of the 16 combinations, this will yield n=48 with a given IP versus n=48 without the given IP (averaging over other combinations of the other three IPs) for the test of each main effect. Based on a two-sample t-test, this will yield 80% power for an effect size of 0.58. For testing any two-IP combination, i.e. yes for the first and second IP (versus no for at least one of those two), this will yield n=24 with a given combination of those two IPs versus n=72 without the given combination of two IP; this yields 80% power to detect an effect size of 0.67.

Similarly, for testing any three-IP combination, this will yield n=12 with a given combination of those two IPs versus n=84 without the given combination of two IP; this yields 80% power to detect an effect size of 0.87. In summary, we have sufficient power for detecting a moderate effect size in each of the above scenarios.

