We will report all baseline characteristics (with counts (%) or mean (SD), median (IQR)) by intervention group, and will follow all reporting guidelines of the CONSORT extension to randomized trials of nonpharmacologic treatment[Boutron 2017], including creating a CONSORT diagram for transparent reporting. The primary analyses for the intervention trial will use an analysis of variance (ANOVA) model[Collins 2014](or equivalently a linear model as defined in Equation 1) with the Likert scale response (1-7, which are expected to be normally distributed) for help-seeking intention as the primary outcome and the assigned treatment factors as the explanatory variables; each $x_j = 1$ if the participant is assigned to the j th IP, and $x_j = 0$ otherwise.

$(1)y = \beta_0 + \beta_1 x_1 + \beta_2 x_2 + \beta_3 x_3 + \beta_4 x_4 + \beta_5 x_1 x_2 + \beta_6 x_1 x_3 + \beta_7 x_1 x_4 + \beta_8 x_2 x_3 + \beta_9 x_2 x_4 + \beta_{10} x_3 x_4 + \beta_{11} x_1 x_2 x_3 + \beta_{12} x_1 x_2 x_4 + \beta_{13} x_1 x_3 x_4 + \beta_{14} x_2 x_3 x_4 + \beta_{15} x_1 x_2 x_3 x_4$ The main effect for the 1st IP, for instance, can then be defined as the contrast testing

$(\beta_1 + \beta_5 + \beta_6 + \beta_7 + \beta_{11} + \beta_{12} + \beta_{13} + \beta_{15}) - (\beta_0 + \beta_2 + \beta_3 + \beta_4 + \beta_8 + \beta_9 + \beta_{10} + \beta_{14}) = 0$, where the first set of 8 coefficients correspond to conditions with $x_1 = 1$, and the second set include $x_1 = 0$. We will also test two- and three-way combinations of the different IPs through similar contrasts. For instance, the test for having both the first and second IP (versus no for at least one of those two, averaging over other IP combinations) will be tested using the following contrast: $(\beta_5 + \beta_{11} + \beta_{12} + \beta_{15}) - (\beta_0 + \beta_1 + \beta_2 + \beta_3 + \beta_4 + \beta_6 + \beta_7 + \beta_8 + \beta_9 + \beta_{10} + \beta_{13} + \beta_{14}) = 0$.

While the linear model and factorial design also allow for testing interactions, e.g. whether the effect of the first IP differs by presence or absence of the second IP, these effects were of less interest for our hypotheses, and will therefore only be considered as exploratory analyses. The other outcome measures and exploratory analyses and can be tested in the same manner with the above linear model. Normality of outcomes will be

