IP 3 Description: Difficulty with garnering parent or guardian support of mental health and LGBTQ status. Finding the words to communicate with their parent, or for themselves regarding names and identities for how they feel. Anticipating dismissal of their concerns and how they can find other supportive adults who can help them navigate communicating with a parent or guardian. Specific resources that they can offer to their parent (i.e. support groups, reading material, professionals) so their parent can receive assistance navigating their child's LGBTQ status instead of them having to educate their parent.

IP 4 Description: Finding affirming professionals. How to identify whether mental health professionals are competent in working with LGBTQ+ youth. Reviewing resources that help to identify mental health friendly spaces online. Reviewing what questions they can ask of a provider or a healthcare setting to know whether they would be affirming. What the law says about conversion therapy.

The research team will moderate all online discussions and provide feedback to individuals to guide them to factual information that can help answer their questions. Individuals will be prompted by text message each week to remind them to contribute to the Discord community.

Follow Up Survey (1 month)

All randomized individuals will receive a follow-up survey 30 days after they complete the baseline survey. Mechanistic and outcome survey constructs will be repeated in this survey. Additionally, in all but Group 1, we will measure Feasibility (i.e. proportion of IP tasks completed, length of time IP used); Usability utilizing the System Usability Scale (SUS); and Acceptability using open-ended questions regarding whether each IP group was helpful, affirming of SGM status, if timing and amount of content were appropriate, if privacy and confidentiality were maintained, and if they had any negative consequences of participation (e.g. parent questioning them).

Participants will be compensated for each research activity as described in compensation.

2. Upload a copy of all materials used to collect data about subjects: (Attach all surveys, interview/focus group scripts, and data collection forms except for case report forms, SCID or KSADS):

Document	Category	Date Modified	Document History
View SMASI (Modified, using items 14-16) (1.0)	Data Collection	6/22/2023	History
View Global Unique Identifier Information.docx(0.01)	Data Collection	2/24/2023	History

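### The printed main-effect and combination contrasts add 0/1-coded coefficients as if they were cell means, so programmed literally they do not test the comparisons the plan describes

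*Combined protocol and SAP*

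**What the plan says.** Study Design, item 8, sets each x_j to 1 if the participant is assigned IP j and 0 otherwise. Equation 1 is the full 2⁴ model: an intercept b0 and 15 further terms. Two contrasts are then printed.

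- **IP1 main effect.** "The main effect for the 1st IP, for instance, can then be defined as the contrast testing" (b1+b5+b6+b7+b11+b12+b13+b15) − (b0+b2+b3+b4+b8+b9+b10+b14) = 0, "where the first set of 8 coefficients correspond to conditions with" x1 = 1.
- **IP1 and IP2 together.** "the test for having both the first and second IP (versus no for at least one of those two, averaging over other IP combinations") is (b5+b11+b12+b15) minus the sum of the other 12 coefficients, again including b0.

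The method is then extended: "We will also test two- and three-way combinations of the different IPs through similar contrasts". Other outcomes "can be tested in the same manner with the above linear model".

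The power paragraph of the same item describes the comparisons in words: 48 v 48 for a main effect, "averaging over other combinations of the other three IPs"; 24 v 72 for two IPs; 12 v 84 for three. The detectable effects at 80% power are 0.58, 0.67 and 0.87.

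Item 8 calls the 1–7 help-seeking response the primary outcome. Item 3 says: "The secondary study endpoint is change in help-seeking intention".

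**The concern.** With 0/1 coding, b0 is the mean of the no-IP group and every other coefficient is an increment. The plan treats the 16 coefficients as if they were the 16 group means. A treatment contrast in this model cannot contain the intercept, and both printed contrasts subtract it.

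If they are programmed as printed, the analysis of help-seeking intention does not test the hypotheses that the sample size was planned for. IPs could be declared effective or ineffective for reasons unrelated to their effects. If an analyst corrects the formula silently, the result is an undocumented departure from the plan.

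**Working it through.** **Inputs from the documents.** 16 cells of 6, N = 96, so 96 − 16 = 80 residual df; 0/1 coding; the printed contrasts; effect sizes 0.58, 0.67 and 0.87. **Assumed.** Two-sided 5% level (not stated, but it reproduces the plan's power figures); mean and SD of the 1–7 item (not given, so varied).

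**The plan's own power.** A two-sample t-test with 94 df gives 80.3% (48 v 48, 0.58), 80.3% (24 v 72, 0.67) and 79.7% (12 v 84, 0.87). The stated figures reproduce, so the comparisons in words are sound.

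**What the printed contrasts estimate under 0/1 coding.** Write m(abcd) for the mean of the cell with x1 = a, …, x4 = d.

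- All 16 coefficients sum to m(1111). Those without x1 sum to m(0111). The IP1 contrast is therefore [m(1111) − m(0111)] − m(0111) = m(1111) − 2m(0111).
- The coefficients containing both x1 and x2 sum to D = m(1111) − m(0111) − m(1011) + m(0011). The two-IP contrast is D − [m(1111) − D] = m(1111) − 2m(0111) − 2m(1011) + 2m(0011).

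The weights sum to 1 − 2 = −1 and to 1 − 2 − 2 + 2 = −1. If no IP works and every cell has mean μ, both contrasts equal −μ. The point estimates use 2 and 4 of the 16 cells; only the error term uses everyone. The squared weights sum to 5 and 13. A three-IP contrast is not printed; built by analogy it has weights summing to −1 and squared weights summing to 29.

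**Rejection rates.** SE = SD × √(sum of squared weights / 6); rejection comes from the noncentral t with 80 df. Example at mean 4, SD 1.5, main effect: SE = 1.5 × √(5/6) = 1.37; −4/1.37 = −2.92; rejection 82%.

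| No IP works (0/1 coding) | Main | Two-IP | Three-IP (by analogy) |
|---|---|---|---|
| Raw score, mean 4, SD 1 | 99% | 77% | 44% |
| Raw score, mean 4, SD 1.5 | 82% | 43% | 22% |
| Raw score, mean 4, SD 2 | 58% | 27% | 15% |
| Raw score, mean 2, SD 2 | 19% | 10% | 7% |
| Change score, mean 0, SD 1.5 | 5% | 5% | 5% |
| Change score, mean 0.5, SD 1.5 | 6.5% | 5.6% | 5.3% |
| Change score, mean 1, SD 1.5 | 11% | 7% | 6% |

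Taking each possible mean on a 1–7 scale with the largest SD it allows, the rate never falls below about 16% (main) or 9% (two-IP). A simulation of 20,000 trials at mean 4, SD 1.5 gave 82.9%, 43.9% and 22.3%.

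**Direction and power under 0/1 coding.**

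- Raw score, mean 4, SD 1.5: a true IP1 benefit of 0.58 SD (0.87 points) moves the contrast from −4 to −3.13, and rejection falls from 82% to 62%.
- Change score, zero elsewhere: noncentrality is 0.58/√(5/6), 0.67/√(13/6) and 0.87/√(29/6), giving power of 10%, 7% and 7% against the planned 80%. The two- and three-IP figures assume an effect only when all the named IPs are present.
- Change score, IP1 inert, IP2 to IP4 each adding 0.58 SD: noncentrality −1.74/√(5/6); the IP1 test rejects 47% of the time.

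**If the coefficients are instead read as the 16 cell means.** The main-effect contrast is valid (weights sum to 0, error 5%). The two-IP contrast has weights summing to 4 − 12 = −8 and squares summing to 16. At mean 4, SD 1.5 its expectation under no effect is −32 with SE 1.5 × √(16/6) = 2.45, so it rejects about 100% of the time. At a mean change of 0.5 it rejects 36%, and at 0 it rejects 5%.

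**The case against.** The strongest reply is that the main-effect error may never operate. Item 8 names ANOVA as the method and offers Equation 1 as an equivalent. A balanced effect-coded ANOVA tests each main effect correctly, and the 48 v 48 wording makes the intent plain. The phrase linking coefficients to conditions also supports the cell-mean reading, under which the main-effect formula is right. That stands: for main effects the harm depends on literal 0/1 programming of the printed sum. It does not cover the two-IP test. The plan commits to the printed contrast for that test, it fails under both readings, and a default ANOVA table does not show the comparison of both against not both. A fitted ANOVA model could produce it, but only as a custom contrast with weights the plan does not give.

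Other points limit the size of the problem. The large error rates belong to the raw score and rest on an assumed mean and SD; on a change score error is 5–11% (main) and 5–7% (two-IP) over mean changes of 0 to 1. The plan also allows transformations and other generalized linear models, under which the rates would differ. The three-IP figures concern a contrast that is only implied. The study is a pilot, and item 3 ranks help-seeking intention as secondary. Nor does the fault reach all of item 3's primary endpoints: "in all but Group 1, we will measure Feasibility", and usability and acceptability carry the same exclusion, so the 16-cell model cannot be fitted to them. These points narrow the reach, but they do not make the printed formulas right.

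**Conclusion.** The concern holds. The algebra needs no assumption: under the stated coding neither printed contrast is the comparison described in words, and the two-IP contrast is wrong under either reading of the coefficients. How large the error would be depends on a mean and SD the documents do not give and on which outcome is analysed. On the raw 1–7 score, error under literal coding is above 5% at any possible mean and SD (floor about 16% main, 9% two-IP; 82% and 43% at mean 4, SD 1.5). On a change score centred at zero the error rate is nominal when no IP works, but power is about 10% and 7% instead of 80%, and the IP1 test responds to the other IPs. Neither outcome gives a usable test. The power calculation itself is unaffected. The text must be corrected before analysis.

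**What to change.** Replace the printed contrasts with differences of cell averages. In the coefficients of Equation 1:

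- **IP1 v no IP1:** b1 + ½(b5+b6+b7) + ¼(b11+b12+b13) + ⅛b15 = 0.
- **IP1 and IP2 v not both:** ⅔(b1+b2) + b5 + ⅓(b6+b7+b8+b9) + ½(b11+b12) + ⅙(b13+b14) + ¼b15 = 0.
- **IP1, IP2 and IP3 v not all three:** 4/7(b1+b2+b3) + 6/7(b5+b6+b8) + 2/7(b7+b9+b10) + b11 + 3/7(b12+b13+b14) + ½b15 = 0.

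The other IPs follow by relabelling. Equivalently, state the contrasts on cell means with weights 1/8 v 1/8, 1/4 v 1/12 and 1/2 v 1/14. The squared weights then sum to 1/4, 1/3 and 4/7; error is 5%, and power with 80 df is 80.2%, 80.2% and 79.5% at 0.58, 0.67 and 0.87.

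Those power figures need all 96 participants analysed. Recruitment Methods, item 3, erases the data of survey non-completers; with 5 per cell (64 df) power is about 72% for all three tests, and with 4 per cell (48 df) about 62%.

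State also whether y is the follow-up 1–7 score or the change from baseline, since items 3 and 8 differ.

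The cost is an amendment to the text and the analysis code, with no new data and no more participants.

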We have developed 4 low-fidelity prototypes to simulate an intervention component without requiring hard coding. We are calling these "mini interventions" IPs or intervention principles.

We will use a factorial trial to understand each IP prototype's individual and combined feasibility, usability, acceptability, and change in help-seeking intention in an online sample of diverse (racially, ethnically, age, gender identity, sexual orientation) sexual and gender minority youth (SGMY).

2. * Describe the relevant prior experience and gaps in current knowledge

including preliminary data. Provide for the scientific or scholarly background for, rationale for, and significance of the research based on existing literature and how it will add to existing knowledge:

Depression and anxiety are leading contributors to adolescent morbidity, and suicide is the second leading cause of death in this age group. However, fewer than half of affected adolescents access treatment. Rates of depression and suicidality are higher among sexual and gender minority youth (SGMY) and they are less likely than other youth to seek care. Although adolescents with depressive symptoms may be identified in school clinics or primary care settings, identification does not always result in treatment. Adolescents with negative beliefs about diagnosis or treatment and lacking social and parental support are less likely to receive treatment. SGMY at risk of depression are especially difficult to reach as they are less likely to attend preventive primary care visits where routine screening is performed. They may have concerns about confidentiality and disclosing their sexual orientation or gender identity to healthcare or mental health providers, and fear rejection, discrimination, or unsupportive environments. A facilitator of mental health help-seeking, parental support, is often lacking in SGMY who experience more severe depression and suicidality. There is a critical need to develop and test interventions that increase the likelihood of seeking evidence-based treatment among SGMY with depression, anxiety, and suicidality in non-clinical settings.

With SGMY actively immersed online, internet-based interventions are an obvious and promising route to meet SGMY where they are. Yet a recent systematic review found a dearth of evidence-based online mental health interventions for SGMY.

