The Discord server is similar to a Microsoft Teams or Slack where there are different channels available for different individuals. Each user, based on which Group they were randomized to will have access to a different set of channels which allow them to view their assigned intervention. All participants will be asked to sign in at least once a week to Discord to review and complete intervention activities and will be prompted with a text message reminder. The Discord settings will be set to not allow private messaging between individuals to allow for monitoring of all content. Each individual will be asked to agree to and review ground rules of participating which include acknowledging that the intervention does not provide crisis services, to maintain anonymity, to not bully, and that any content our team feels will be hurtful to others will be removed. The research team will download and save Discord transcripts from text conversations.

There are four "mini-interventions" or IPs: IP1, IP2, IP3, IP4.

There will be 16 groups with iterations of these interventions as described below:

Group 1: No IP, only a specific discord channel that asks individuals to at least post once a week responding to a single question about what makes them interested in participating in research

Group 2: IP 1

Group 3: IP 1, IP2

Group 4: IP 1, IP 2, IP 3

Group 5: IP 1, IP 2, IP 4

Group 6: IP 1, IP 2, IP 3, IP 4

Group 7: IP 1, IP 3

Group 8: IP 1, IP 3, IP 4

Group 9: IP 1, IP 4

Group 10: IP 2

Group 11: IP 2, IP 3

Group 12: IP 2, IP 3, IP 4

Group 13: IP 2, IP 4

Group 14: IP 3

Group 15: IP 3, 4

Group 16: IP 4

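### The with-IP versus without-IP model does not suit feasibility, a primary endpoint that has no value without the IP or depends partly on how many IPs were assigned

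*Combined protocol and SAP*

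**What the plan says.** Study Aims item 1 gives the purpose: "We will use a factorial trial to understand each IP prototype's individual and combined feasibility, usability, acceptability, and change in help-seeking intention". Study Design item 3 sets the rank of the endpoint: "The primary endpoints are feasibility, usability, and acceptability of the IP".

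The Follow Up Survey part of Research Activities item 1 defines the measure and who has it: "in all but Group 1, we will measure Feasibility (i.e. proportion of IP tasks completed, length of time IP used". It does not say whether the measure is taken per person or per IP, what the denominator of the proportion is, or how time is captured.

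Study Design item 8 specifies a linear model (Equation 1) for help-seeking intention with "the assigned treatment factors as the explanatory variables": four 0/1 indicators and all their interactions, 16 coefficients in total. The main effect of an IP compares all conditions that include it with all conditions that do not. For everything else, item 8 says: "The other outcome measures and exploratory analyses and can be tested in the same manner with the above linear model". It gives no feasibility benchmark, no term for the number of IPs and no rule for Group 1.

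Two parts of the Intervention description matter here. Every IP has the same three-channel format, so content grows with each IP assigned. The requested exposure does not grow with it: "All participants will be asked to sign in at least once a week to Discord to review and complete intervention activities".

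**The concern.** A with/without contrast works for help-seeking intention because everyone has an intention score whatever they were assigned. Feasibility is different: it describes use of the assigned content. People not assigned an IP have no completion or time value for it. A person-level total or proportion exists for everyone in Groups 2 to 16, but it mixes how well an IP was taken up with how much the person was given.

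At stake is whether the trial can answer its first aim, which IPs are feasible alone and together. A significant contrast could be read as evidence about an IP when it partly reflects the number of IPs assigned, and a null contrast could be equally uninformative.

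**Working it through.** **Inputs.** From the plan: 16 groups of 6; an IP is present in 8 groups (48 people) and absent in 8 (48 people); Group 1 has no feasibility measure. Assumed, because the plan gives none: two-sided 0.05, no dropout, and all usage means, coefficients of variation (CV) and task counts.

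**Plan's own figure.** 48 versus 48 at effect size 0.58 gives 80.3% power by the noncentral t, so the stated 80% reproduces. It applies to an outcome measured in all 16 groups; without Group 1 the comparison is 48 versus 42.

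**Assigned content by arm.** The 8 groups with a given IP hold 1, 2, 2, 2, 3, 3, 3 and 4 IPs: 20/8 = 2.50. The 8 without it hold 0, 1, 1, 1, 2, 2, 2 and 3: 12/8 = 1.50. Dropping Group 1 gives 12/7 = 1.71.

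**Total time, additive use.** Let m_j be mean time on IP j and S the summed mean time on the other three. The with-IP cells average m_j + S/2. The without-IP cells average S/2 if Group 1 is scored zero, or 4S/7 if it is left out. The contrast is therefore m_j, or m_j − S/14. With four equally used IPs (S = 3m) the latter is m(1 − 3/14) = 0.79m. A zero null for time thus asks roughly whether the IP was used at all.

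**Proportion of assigned tasks, fixed effort.** Suppose everyone does 6 tasks and each IP has 12. The proportions for 1 to 4 IPs are 50%, 25%, 16.7% and 12.5%.
- With the IP: (50 + 3×25 + 3×16.7 + 12.5)/8 = 23.4%.
- Without it, Group 1 excluded: (3×50 + 3×25 + 16.7)/7 = 34.5%.
- Difference: about −11 points for every IP, although all four are identical.

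**Simulated rejection rates.** Groups 2 to 16, 6 per group, four identical IPs, 1,500 to 3,000 runs per scenario:

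| Assumed behaviour | Component | Rejects zero |
|---|---|---|
| Additive use, times independent across IPs, CV 0.5 / 1 (cell-mean contrast) | Total time | 100% / 74% |
| Additive use, person and IP CV both 0.3 / 0.5 / 0.75 / 1.0 (four-indicator linear model) | Total time | 100% / 92% / 57% / 34% |
| Same, two-sample t-test | Total time | 96% / 67% / 34% / 20% |
| Fixed effort per person | Total time | about 5% |
| Fixed effort, mean 6 tasks, 12 per IP, CV 0.5 / 1 (cell-mean contrast) | Proportion of assigned tasks | 94% / 51%, about −11 / −9 points |
| Equal completion whatever the load | Proportion of assigned tasks | 4–6% |
| Completion falls 5 / 10 points per extra IP (linear model) | Proportion of assigned tasks | about 17% / 53% |

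**Can the contrast still rank IPs?** Under additive use, four-indicator coefficients recover about 1.0, 0.5 and 0.1 for a fully, half and barely used IP. At CV 0.3 / 0.5 / 0.75 / 1.0 the half-used IP still rejects zero in 89% / 48% / 25% / 14% of runs; the barely used one rejects in 5–11%. Power to tell a fully used from a half-used IP is 65% / 26% / 14% at CV 0.3 / 0.5 / 0.75.

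**Can Equation 1 be fitted?** Without Group 1 there are 15 observed cells for 16 coefficients. The design matrix has rank 15, so the model is not estimable as written.

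**The case against.** The best defence has four parts.

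First, item 8 says other outcomes can be tested this way; it does not say they will be, and it never names feasibility. The sentence may refer only to the repeated survey constructs. That stands as a reading, but then a primary endpoint has no stated analysis, and the same change is needed.

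Second, a reader might infer that the test rejects by construction for any IP. The documents do not support this. Under equal completion of assigned tasks the proportion test rejects at its nominal rate, and under a fixed time budget so does the time test. The weekly sign-in is a minimum, not a cap on effort, so the plan does not imply that an extra IP must lower completion.

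Third, a reader might infer that the trial would report every IP as raising time and lowering completion. The high rejection rates for those two results come from opposite assumptions, additive use and fixed effort, and behaviour between the two was not simulated. What remains is that under either assumption one of the two components follows the number of IPs assigned.

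Fourth, a reader might infer that the IPs could not be ranked. Under additive use they can be, though imprecisely. A fall in completion with load would also be a genuine finding about combined feasibility; the difficulty is that this contrast attributes it to each IP separately.

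**Conclusion.** The concern holds in this limited form: the with/without contrast is a poor fit for feasibility, and the plan offers no other analysis or benchmark for it. Measured per IP, there is no comparison group. Measured per person, the arms differ by 1.00 assigned IP on average (0.79 without Group 1), and time or proportion completed can reflect that difference. For time, rejecting zero shows use, not feasibility.

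The arm imbalance and the rank deficiency follow from the design alone. The rejection rates, about 5% to 100%, rest on assumed behaviour and variability and should not be read as a forecast. Usability is a separate endpoint with its own scale and is not part of this point. The analysis of feasibility should be changed; nothing here affects the model for help-seeking intention, where Group 1 is measured.

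**What to change.** In Study Design item 8, take feasibility out of the Equation 1 contrasts and specify instead:

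- **Individual feasibility.** For each IP, among the 48 people assigned to it, report the proportion of that IP's own assigned tasks completed and the time spent on that IP, each with a 95% confidence interval. State the denominator.
- **Combined feasibility.** Within those 48, regress each IP-specific measure on the number of co-assigned IPs (0, 1, 2 or 3, held by 6, 18, 18 and 6 people). The slope is the load effect.
- **Comparison of IPs.** Compare IPs within person among those assigned two or more (11 groups, 66 people).

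Costs: there is no with/without p-value for feasibility. Precision is limited: a yes/no rate on 48 people has a 95% interval of up to 1.96 × √(0.25/48) = ±14 points, before dropout. The change is mostly wording, but not entirely. Each IP has its own channels and Discord text transcripts are saved, so posted tasks can be counted by IP. Transcripts do not show viewing or reading time, so time has to be recorded by IP, and the plan should say how.
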